### **Data Analysis Plan:**

The data analysis plan for the study will be as follows. The primary analysis will be intention-to-treat, with the primary endpoint being change in PA lumbar spine aBMD. Statistical significance will be defined as a two-tailed p-value of  $\leq 0.05$ .

Phase 1 Aims 1-3: Baseline mean clinical characteristics between the 2 groups will be compared by t-test. Variables will be tested for normality using the Shapiro-Wilk test, and if non-normal, variables will be log-transformed before analysis. If the distribution remains non-normal after log-transformation, nonparametric testing using the Wilcoxon rank sum test will be performed instead. The analysis of variables at 12 months will be performed using a linear random effects model to estimate and test the effects of the 2 randomization groups (romosozumab vs placebo) from baseline to 12 months on the study endpoints.

Phase 1 Aim 4: The analysis of variables at 12 months will be performed using a linear random effects model to estimate and test the effects of the 2 randomization groups (romosozumab vs placebo) from baseline to 12 months on the study endpoints. We will also add a lean body mass x randomization group interaction term to examine if the effects of body mass change differ between romosozumab and placebo.

Phase 2 Aim 1: The analysis of variables at 24 months will be performed using a linear random effects model to estimate and test the effects of the 2 randomization groups (12 months of romosozumab followed by a single intravenous infusion of open-label zoledronic acid vs 12 months of placebo followed by a single intravenous infusion of open-label zoledronic acid) from baseline to 24 months on the study endpoints.

Phase 2 Aim 2: A secondary analysis will be performed to determine whether gains achieved in the romosozumab group are maintained through the subsequent 12-month study period using a linear random effects model with the fixed effect being time and the random effect being the intercept. Lack of statistical significance will indicate maintenance (lack of decrease--or increase) of BMD.

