## II. Specific Aims

### Phase 1: Romosozumab vs placebo

This █-sponsored investigator-initiated protocol is a randomized, double-blind, placebo-controlled clinical trial which aims to investigate the effect of romosozumab on BMD in women with anorexia nervosa. We will also investigate the safety of romosozumab in women with anorexia nervosa. We hypothesize that 12 months of romosozumab administration will result in an increase in bone mineral density, increase in markers of bone formation and decrease in markers of bone resorption, and improvement in bone microarchitecture in osteopenic women with anorexia nervosa compared with placebo.

**Specific Aim 1:** We hypothesize that 12 months of romosozumab administration will result in an increase in bone mineral density in women with anorexia nervosa with low bone mass or osteoporosis compared with placebo.

We will investigate in women with anorexia nervosa in a 12-month study whether treatment with romosozumab will increase BMD as measured by dual energy x-ray absorptiometry (DXA) compared with placebo. The primary endpoint will be change in lumbar spine BMD from baseline to 12 months. Bone density will be measured at baseline, 6 months and 12 months.

**Specific Aim 2:** We hypothesize that 12 months of romosozumab administration will result in a significant increase in markers of bone formation and reduction of markers of bone resorption in osteopenic women with anorexia nervosa compared with placebo.

We will investigate in women with anorexia nervosa in a 12-month study whether markers of bone formation, including osteocalcin and P1NP, will increase in the romosozumab group more than in the placebo group. We will also investigate whether markers of bone resorption, including CTx, will decrease in the romosozumab group more than in the placebo group. Markers of bone metabolism will be measured at baseline, 3 months, 6 months, 9 months and 12 months.

**Specific Aim 3:** In this exploratory aim, we hypothesize that 12 months of romosozumab administration will result in improved bone microarchitecture and strength in osteopenic women with anorexia nervosa compared with placebo.

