## VI. Biostatistical Analysis

**Sample Size and Justification:** Group sample sizes of 20 (active therapy) to 10 (placebo) for a total N=30 will achieve 80% power to reject the null hypothesis of equal means when the population mean difference is at least 9% with a standard deviation between groups of 8% and with a significance level of (alpha) of 0.050 using a 2-sided 2-sample equal-variance t-test. This is based on the difference in percent change in spine bone density between the romosozumab (n=65) and placebo (n=61) groups in Cosman F. *et al.*.

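### The Phase 1 primary model has no stated covariance; if a random intercept is fitted to the 0/6/12-month BMD, type I error could be about 9–16% instead of 5%

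*Combined protocol and SAP*

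**What the plan says.** The Data Analysis Plan (section VI) covers Phase 1 Aims 1–3 with one model sentence: "The analysis of variables at 12 months will be performed using a linear random effects model", used to estimate and test the effect of the two randomized groups from baseline to 12 months. It states no random effects, time coding, within-woman covariance, degrees-of-freedom method or tested contrast. It does not say whether the month-6 scan enters the model.

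The plan describes a random-effects structure in one place only, Phase 2 Aim 2: "with the fixed effect being time and the random effect being the intercept". That is a one-arm secondary analysis of BMD at months 12 and 24.

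The visit lists differ by aim. Phase 1 Aim 1 says "Bone density will be measured at baseline, 6 months and 12 months". Phase 1 Aim 4 lists lumbar spine BMD at 0 and 12 months only, and Phase 2 Aim 1 lists baseline and 24 months only.

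The error rate is fixed by "Statistical significance will be defined as a two-tailed p-value of" 0.05 or less. The sample size section uses a different procedure, a two-sample t-test on percent change: "Group sample sizes of 20 (active therapy) to 10 (placebo) for a total N=30", which "will achieve 80% power to reject the null hypothesis of equal means".

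**The concern.** A random intercept treats each woman's deviations at 0, 6 and 12 months as exchangeable around her own level. That does no harm with two visits. With three visits, the model uses one pooled residual variance for two different quantities: the 0–12 month change, and the departure of month 6 from the midpoint of months 0 and 12. If women differ in how fast their BMD changes, the first varies more than the second. Pooling then understates the variance of the change. With complete data the estimated group difference in change is unaffected, but its standard error and p-value are not.

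The test at stake is the Phase 1 primary endpoint. As written, the plan allows both an analysis that holds 5% and one that may run at two to three times that rate. Nothing fixes the choice before the data are seen.

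**Working it through.** **Inputs from the documents.** 20 vs 10 women; two-sided alpha 0.05; SD of 12-month change 8% and difference 9% (Sample Size and Justification); BMD at 0, 6 and 12 months (Phase 1 Aim 1); DXA spine precision 0.01 g/cm² (Methods).

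**Assumptions.** No mean BMD is given. At 0.8–1.0 g/cm², the stated precision is 0.01/1.0 = 1.0% to 0.01/0.8 = 1.25%. A visit-level SD of 3% is added as a generous upper case. The within-woman covariance is not given, so three shapes are tried. Data are taken as complete.

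**Step 1: the plan's own figure.** Noncentrality = 9 / (8 × √(1/20 + 1/10)) = 9 / 3.098 = 2.905 on 28 df. Power is 80.06%, so the stated 80% reproduces.

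**Step 2: what the random intercept does to the standard error.** Let L = (y12 − y0)/√2 and Q = (y0 − 2·y6 + y12)/√6. With balanced data and categorical visit, the random-intercept model estimates the variance of L by about (Var L + Var Q)/2. So

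model SE / correct SE = √[(Var L + Var Q) / (2 Var L)].

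Var L = 8²/2 = 32 throughout. With visit-level SD m:

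- Random slopes: Var Q = m². At m = 1.25, √[(32 + 1.56)/64] = 0.724. At m = 3, √[(32 + 9)/64] = 0.800.
- Random walk, or all real change complete by month 6: Var Q = m² + (64 − 2m²)/6. At m = 1.25, √[(32 + 11.71)/64] = 0.826. At m = 3, √[(32 + 16.67)/64] = 0.872.

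The ratio is 1 only when m² = 32, that is m = 8/√2 = 5.7%.

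**Step 3: type I error.** Null simulation, 40,000 trials per scenario, random intercept on 0/6/12 data (categorical / linear time):

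| Visit-level SD | Random slopes | Random walk | Change complete by month 6 |
|---|---|---|---|
| 0 | 16.9 / 17.7% | 10.9 / 11.2% | 11.2 / 11.2% |
| 1.25% | 15.5 / 16.1% | 10.4 / 10.7% | 10.7 / 10.8% |
| 3% | 11.6 / 12.0% | 8.5 / 8.7% | 9.0 / 9.1% |
| 4% | 8.9 / 9.1% | 7.3 / 7.4% | 7.6 / 7.6% |
| 5.66% | 5.0 / 5.0% | 5.0 / 5.0% | 5.1 / 5.1% |

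Testing the 0–12 change with its own variance gave 4.8–5.2% in every scenario. Fitting the mixed model directly at m = 1.25% (400 trials per scenario, Monte Carlo SE about 1.5–2 points) gave 17.3% for slopes and 9.3% for the random walk, in line with the table.

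**Step 4: sensitivity to the 8%.** With an SD of 12-month change of 3–5% and m = 1.25%, type I error is 8.4–14.8%, so the inflation does not depend on the 8% alone.

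**The case against.** A reader might infer that the plan commits Phase 1 to a random intercept and so has a 9–16% error rate. The documents do not support that. The intercept is written for Phase 2 Aim 2, where two time points make it adequate, and no random effects are assigned to Phase 1. Nor does the plan say that month 6 enters the primary model. The endpoint is a 0–12 month change, the analysis is described as being of variables at 12 months, and nearly the same model sentence serves aims with only two listed times. On months 0 and 12 alone, a random intercept reproduces the t-test on change and holds 5%. The true covariance is also undocumented, and under compound symmetry the three-visit fit holds 5% as well.

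All of this stands, and it makes the finding conditional. It does not remove it. Aim 1 lists three visits where Aim 4 and Phase 2 Aim 1 list two, and an analyst looking for a structure finds only the intercept. The 5% case on three visits needs a visit-level SD near 5.7%, four to five times the stated DXA precision at the assumed BMD. Aim 4 itself expects women to differ in BMD gain.

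A second tempting inference is that the bone markers do worse because they have more visits: "Markers of bone metabolism will be measured at baseline, 3 months, 6 months, 9 months and 12 months". The same question of structure arises there, but the documents give no marker variability, so no error rate can be attached. It would also overstate matters to call this the trial's only confirmatory test: the study is titled a pilot, and Phase 2 has its own primary endpoint.

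**Conclusion.** The concern holds in conditional form. The Phase 1 primary model is under-specified, and a natural way of filling the gap, a random intercept on all three BMD visits, could give about 9–16% type I error instead of 5%. That range rests on the plan's 8% SD of change, an assumed visit-level SD of 1.25–3%, complete data, and real differences between women in BMD change that follow slopes, a random walk or an early plateau. The full conditional range is 5% to about 17% (17.7% with linear time). The plan gives no dropout rate, and dropout was not modelled. The stated 80% power is correct for the t-test, but that is not the model named for analysis.

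**What to change.** State for Phase 1 Aims 1–3, before unblinding: a repeated-measures model with visit as a categorical factor, group-by-visit interaction, unstructured within-woman covariance and Kenward-Roger degrees of freedom, and name the visits included. Define the primary test as the group difference in change from baseline to month 12, that is, the month-12-minus-baseline group-by-visit contrast.

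The contrast needs that wording. If baseline is one of the outcomes, a plain comparison of month-12 means carries the between-woman variance. Assuming a baseline SD of 8–15% and change independent of baseline, the SD rises from 8% to √(64 + 64) = 11.3% or √(225 + 64) = 17%, and power falls from 80% to about 51% or 26%.

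A t-test or baseline-adjusted ANCOVA on the 12-month change is an acceptable simpler choice. With complete data and the outcome on the same percent scale, the repeated-measures contrast matches the t-test used for sizing. The random intercept can stay where exactly two time points are analysed, as in Phase 2 Aim 2.

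The cost is a sentence or two in the plan and a few more covariance parameters. No visit, scan or sample size changes.

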## **Phase 1 Endpoints:**

### **Primary:**

Change from baseline to 12 months in lumbar spine bone mineral density by dual energy x-ray absorptiometry (DXA).

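### The primary between-group model specifies no adjustment for baseline lumbar spine BMD, although the 20:10 trial is small and not stratified on BMD

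*Combined protocol and SAP*

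**What the plan says.** Section VI, Data Analysis Plan, defines the primary endpoint: "The primary analysis will be intention-to-treat, with the primary endpoint being change in PA lumbar spine aBMD". For Phase 1 Aims 1-3 the analysis is a "linear random effects model to estimate and test the effects of the 2 randomization groups (romosozumab vs placebo) from baseline to 12 months". The text lists no fixed effects beyond group, no covariates and no random-effects structure for this model. It does not say whether the response is a change score or the repeated BMD values, or whether the arms share a baseline mean. Apart from the change itself, the only stated use of baseline data for these aims is a t-test comparing the groups' characteristics, which describes imbalance but does not adjust for it. Phase 2 Aim 1 is worded in the same way for 24 months.

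The Sample Size and Justification paragraph states: "Group sample sizes of 20 (active therapy) to 10 (placebo) for a total N=30 will achieve 80% power". The calculation is made "using a 2-sided 2-sample equal-variance t-test", and its source is a comparison of percent change: "This is based on the difference in percent change in spine bone density between the romosozumab (n=65) and placebo (n=61) groups".

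Section V stratifies randomization by BMI (18.5 kg/m² and above, or below), not by BMD. Section II schedules DXA at baseline, 6 and 12 months, so the baseline value is already collected.

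**The concern.** With only 10 placebo women, the arms can differ appreciably in baseline BMD by chance. If baseline predicts change, part of that difference passes into an unadjusted estimate of the treatment effect. A prespecified adjustment removes the linear part of this and may sharpen the estimate, using a measurement the trial already has. If the rule is left open, an adjustment chosen after unblinding could be called data-driven. The baseline t-test does not close the gap: at these sample sizes it reaches p = 0.05 only at an imbalance of roughly 0.79 SD (2.048 × 0.387).

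**Working it through.** **1. The plan's own figure.** Inputs from Sample Size and Justification: n = 20 and 10, difference 9, SD 8, two-sided alpha 0.05.
- SE = 8 × √(1/20 + 1/10) = 3.098
- Noncentrality = 9 / 3.098 = 2.905, with 28 df
- Noncentral t power = 80.06%. The stated 80% reproduces.

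**2. Validity without adjustment.** In 40,000 simulated trials per setting, with baseline-change correlations from 0 to 0.5, the unadjusted test rejected a true null in 4.9% to 5.1% of trials. Its mean estimate was 9.0 when the true difference was 9.

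**3. Size of chance imbalance.** The SE of the baseline difference is √(1/20 + 1/10) = 0.387 SD. Ignoring the BMI stratification, an imbalance above 0.5 SD in either direction has probability of about 20%.

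**4. What an imbalance does.** Let s0 and s1 be the baseline and month-12 SDs, r their correlation, and b = r × s1/s0 the slope of month-12 on baseline. A baseline difference D shifts a change-score estimate by (b − 1) × D. The shift is zero when b = 1.

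**5. Assumptions.** The documents give no s0, s1 or r. I take s0 as 10%, 13% or 16% of mean BMD and treat BMD as a percentage of that mean, so that the plan's SD of 8 applies to the change. Then s0² + s1² − 2·r·s0·s1 = 64 fixes r. The baseline-change correlation is (b − 1) × s0/8; call its size ρ. Adjusted power uses residual SD 8√(1 − ρ²), 27 df, and a variance factor of 1 + 1/26 for estimating the slope.

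| s0 → s1 | r | slope b | ρ | shift from a 1-SE imbalance (points) | adjusted power |
|---|---|---|---|---|---|
| 10 → 10 | 0.68 | 0.68 | 0.40 | 1.2 | 85% |
| 13 → 13 | 0.81 | 0.81 | 0.31 | 1.0 | 82% |
| 16 → 16 | 0.875 | 0.875 | 0.25 | 0.8 | 81% |
| 10 → 11 | 0.71 | 0.79 | 0.27 | 0.8 | 81% |
| 13 → 14 | 0.83 | 0.89 | 0.18 | 0.6 | 80% |
| 16 → 17 | 0.88 | 0.94 | 0.12 | 0.4 | 79% |

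Worked example, first row: r = 1 − 64/(2 × 100) = 0.68, and the shift is (1 − 0.68) × 10 × 0.387 = 1.24 points, or 14% of the 9-point target. In the third row, (1 − 0.875) × 16 × 0.387 = 0.77 points, or 9%.

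**6. Power directly by ρ.** Against 80.1% unadjusted, adjusted power is 78.5% at ρ = 0, 78.9% at 0.1, 80.1% at 0.2, 82.1% at 0.3, 85.0% at 0.4 and 88.7% at 0.5. Break-even is near ρ = 0.2. The worst case is a loss of 80.1 − 78.5 = about 1.5 points.

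**The case against.** The strongest reply is that nothing is broken. Randomization makes the unadjusted estimate unbiased on average, the test holds its level, and the planned power is correct on its own terms. A one-standard-error imbalance moves the estimate by 0.8 to 1.2 points under equal variances. That is 0.25 to 0.40 of the treatment SE of 3.1, and the interval already allows for this variation. All of this stands. The case for adjustment rests on precision and on the bias in the particular allocation obtained.

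Four stronger readings are tempting, and the documents do not support them.

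- A reader might infer that baseline enters only to form a change score. The model is underspecified: a repeated-measures version with a common baseline mean also fits the text and would adjust for baseline.
- A reader might infer that the model simply repeats the planning t-test. With free baseline means, a random intercept and complete data, the point estimate would match. Residual variance would be pooled over three visits, however, so the standard error and degrees of freedom need not match.
- A reader might infer that any pre-post correlation below 1 makes a change score over-correct. The slope decides. With s0 = 10, s1 = 12.8 and r = 0.78, the SD of change is still 8 but the slope is 1, and imbalance causes no shift.
- A reader might infer that the plan forfeits power, or that adjustment is free. Both depend on a correlation the documents do not give. Equal variance is not a safe default: entry requires a BMD Z-score below −1.0, which truncates the baseline spread, and varied response to the drug could widen the month-12 spread.

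**Conclusion.** The point holds as an inexpensive improvement to an incomplete specification, not as an error that invalidates the analysis. That the text names no baseline adjustment is plain, and that the unadjusted test is sound is confirmed by calculation. The size of the benefit is conditional. Under equal variances and a baseline SD of 10% to 16%, power rises by 1 to 5 points; with a month-12 SD one point larger, the effect runs from a gain of about 1 point to a loss of about 1. The balance still favours adjustment: the downside is bounded at about 1.5 points, the gain reaches about 9 points at ρ = 0.5, and the linear effect of whatever imbalance occurs is removed. No size is claimed for the bone markers, because the documents give nothing from which to derive one.

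**What to change.** In the Data Analysis Plan, state that each between-group model for Phase 1 Aims 1-3 and Phase 2 Aim 1 adjusts for the baseline value of its own endpoint. Either of two forms will do, and the plan should name one:

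- baseline as a covariate, with a baseline-by-visit term; or
- baseline kept as an outcome, with the two group means constrained equal at baseline.

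In the same place, state the response and its scale (absolute or percent) and the group and visit terms. Make the adjusted difference at month 12 (month 24 for Phase 2) primary and report the unadjusted change as supportive. Settle this before unblinding.

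The cost is a sentence or two of text, one degree of freedom and, at worst, about 1.5 points of power. It needs no new data, visits or participants.

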We will investigate in women with anorexia nervosa in a 12-month study whether treatment with romosozumab will improve bone microarchitecture, as assessed by HR-pQCT, and improve bone strength, as estimated by microfinite element analysis compared with placebo. HR-pQCT of the tibia and radius will be performed and the following will be measured: trabecular thickness and spacing; cortical thickness and porosity; ITS (individual trabecula segmentation); finite element analysis modeling of bone strength. HR-pQCT will be measured at baseline, 6 months and 12 months.

**Specific Aim 4:** In this exploratory aim, we hypothesize that increases in bone mineral density will be greater in women with anorexia nervosa randomized to romosozumab who gain lean mass over 12 months compared to women randomized to romosozumab who do not gain lean mass over 12 months, and lowest in women randomized to placebo.

We will investigate in women with anorexia nervosa in a 12-month study whether increases in lean mass over 12 months are associated with a greater effect of romosozumab in increasing bone mineral density. It is known that muscle has an anabolic effect on bone through mechanical loading and muscle-bone hormonal cross-talk. Low lean body mass has been associated with impaired bone mineral density, bone microarchitecture, and estimated bone strength in women with anorexia nervosa . Although studies have demonstrated that women continue to have reduced bone mineral density years after the onset of recovery from anorexia nervosa , we hypothesize that the beneficial effects of romosozumab will be greater in women who gain lean mass during the 12 months of the study. We are exploring an association between lean body mass gain and BMD gain, and not causality. Lean mass and LS BMD will be measured by DXA at 0 and 12 months.

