### **Exploratory:**

Change from baseline to 12 months in HR-pQCT variables at the tibia and radius—trabecular thickness and spacing, and cortical thickness and porosity; change from baseline to 12 months in ITS variables; change from baseline to 12 months in finite element analysis modeling of bone strength.

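### Exploratory Aim 4 asks two questions, an ordering and effect modification; the planned lean-mass by group interaction answers only the second (low priority)

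*Combined protocol and SAP*

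**What the plan says.** Specific Aim 4 (II. Specific Aims, Phase 1) opens with an ordering. It predicts a larger BMD increase for "women with anorexia nervosa randomized to romosozumab who gain lean mass over 12 months compared to women randomized to romosozumab who do not", and the sentence ends "who do not gain lean mass over 12 months, and lowest in women randomized to placebo". The explanatory paragraph then puts a different question: "whether increases in lean mass over 12 months are associated with a greater effect of romosozumab in increasing bone mineral density". It calls the aim exploratory, disclaims causality, and fixes the measurements: "Lean mass and LS BMD will be measured by DXA at 0 and 12 months".

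The Data Analysis Plan for Phase 1 Aim 4 (VI. Biostatistical Analysis) has two elements. One is a mixed model whose purpose is given as "to estimate and test the effects of the 2 randomization groups (romosozumab vs placebo) from baseline to 12 months on the study endpoints". The other is the interaction: "We will also add a lean body mass x randomization group interaction term to examine if the effects of body mass change differ", meaning from one arm to the other. It names no within-romosozumab contrast, no comparison of romosozumab non-gainers with placebo, and no definition of a gainer. It does not say whether the covariate is lean-mass level or change, and it moves from lean body mass to body mass change within one sentence.

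**The concern.** The ordering contains two comparisons: gainers with non-gainers inside the romosozumab arm, and romosozumab non-gainers with placebo. Neither of the two planned quantities is either of these. The overall group effect mixes romosozumab gainers and non-gainers. The interaction compares the lean-mass association between arms.

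The pattern that separates them is plausible on the protocol's own rationale. Aim 4 argues that muscle is anabolic to bone through loading and hormonal cross-talk. If that works similarly in both arms, the slopes are similar and positive, the within-romosozumab part of the ordering is true, and the interaction is near zero. A reader holding only the planned interaction could then conclude that Aim 4 was not supported. If the missing contrasts are chosen only after unblinding, they carry less weight.

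**Working it through.** **Inputs from the documents.** 20 romosozumab and 10 placebo; difference 9%, SD 8% (percent change in spine BMD); two-sided alpha 0.05 (section VI, sample size paragraph).

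**The plan's own figure.** "Group sample sizes of 20 (active therapy) to 10 (placebo) for a total N=30 will achieve 80% power": noncentrality = 9 / (8 × √(1/20 + 1/10)) = 2.905 on 28 df, giving power 80.06%. The stated 80% reproduces. The documents give no figure for Aim 4.

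**Algebra (no assumed sizes needed).** Denote by rG, rN, pG and pN the mean BMD change in romosozumab gainers and non-gainers and placebo gainers and non-gainers.

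- Interaction = (rG − rN) − (pG − pN).
- Ordering, part 1 = rG − rN.
- Ordering, part 2 = rN − placebo mean.

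Example with rG 11, rN 7, pG 2, pN −2: part 1 = +4, part 2 = 7 − 0 = 7, interaction = 4 − 4 = 0. The ordering holds and the interaction is null.

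Example with rG 9, rN 9, pG −2, pN 2: part 1 = 0, interaction = 0 − (−4) = +4. The interaction is positive with no difference between romosozumab gainers and non-gainers.

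In regression form, with BMD change = b0 + b1·group + b2·L + b3·group·L and L the lean-mass change, the interaction is b3 and the within-romosozumab slope is b2 + b3. One fit gives both, provided the outcome is BMD change and L has its own main effect.

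**Illustration (slopes and lean-mass distribution are assumptions).** L is standardised to mean 0, SD 1; group effect 9; no dropout; least squares on 26 df; 20,000 trials per scenario. The residual SD is set so that the pooled within-arm SD stays at 8: √(64 − (19·bR² + 9·bP²)/28), where bR and bP are the arm slopes. At bR = bP = 4 this is √(64 − 16) = 6.93.

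| Equal slope in both arms (points per SD) | Interaction rejects | Within-romosozumab slope rejects |
|---|---|---|
| 1 | 5% | 8% |
| 2 | 5% | 19% |
| 4 | 5% | 65% |
| 6 | 5% | 99% |

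The 5% is type I error by construction, because the true interaction is zero. At slope 4 the within-romosozumab rejection rate is 93% if the total SD is 6 and 32% if it is 12. Mean 95% CI half-widths at slope 4 and total SD 8 are 3.4 points per SD for the romosozumab slope, 5.2 for the placebo slope and 6.2 for the interaction.

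**Choosing the contrast for placebo lowest.** Equal slopes of 4, group effect 9:

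- Difference between arms at exactly zero lean-mass change: 9.0.
- Romosozumab women with L ≤ 0 minus all placebo women, mean L = 0: average L below zero is −0.798, so 9 + 4 × (−0.798) − 0 = 5.8.
- The same with mean L = +0.5 SD: average L below zero is −0.641, so 9 + 4 × (−0.641) − 4 × 0.5 = 4.4.

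The difference at zero change would overstate support for the ordering. Non-gainers minus all placebo is the quantity the aim describes. If half the romosozumab women do not gain lean mass, its SE is about 8 × √(1/10 + 1/10) = 3.58, and its CI half-width about 2.10 × 3.58 = 7.5 points (18 df).

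**The case against.** The best reply is that Aim 4 is also worded as effect modification, more than once, and the interaction is the right quantity for that. This stands. A reader might infer that the planned interaction is the wrong analysis for Aim 4; the documents do not support that, because the aim states two questions and the plan covers one.

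A reader might also treat a positive interaction driven by a negative placebo slope as a false positive. With a romosozumab slope of 0 and a placebo slope of −4 or −6, the interaction is significantly positive in 22% or 46% of simulated trials. But the romosozumab effect really is larger in gainers there, so this correctly answers the second question. It also requires placebo women who gain lean mass to do worse on BMD, against the protocol's premise.

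The exploratory endpoint list, which ends with "change from baseline to 12 months in ITS variables; change from baseline to 12 months in finite element analysis modeling of bone strength", has no Aim 4 entry. Little follows: the Aim 4 outcome is lumbar spine BMD change, already the Phase 1 primary endpoint, and endpoint lists name outcomes rather than contrasts.

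Nor does the plan forbid reporting the arm-specific slopes, and a careful analyst might do so; it simply does not commit to it. Finally, the larger slopes are strong assumptions: at total SD 8, a slope of 4 means lean-mass change explains 16/64 = 25% of within-arm variance. At slopes of 1 or 2 the recommended contrast rejects only 8% or 19%, so it may well be inconclusive too.

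**Conclusion.** The point holds in limited form and at low priority. The planned interaction answers the effect-modification question and not the ordering stated first. The overall group comparison does not fill the gap, because it never sets romosozumab non-gainers against placebo. That conclusion is algebraic and rests on no assumed figure. The rejection rates and interval widths depend on assumed slopes, SD and lean-mass distribution, and are illustrative only.

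The needed estimates come from the same fit only if BMD change is the outcome and lean-mass change has a main effect, which the plan leaves open. The aim is exploratory and associational in 30 women; the primary endpoint, its analysis and the sample size are untouched.

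**What to change.** In the Phase 1 Aim 4 paragraph of the Data Analysis Plan:

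1. Keep the interaction, labelled as the analysis of effect modification.
2. State the outcome as 0–12 month change in lumbar spine BMD and the covariate as 0–12 month change in DXA lean mass, with main effects for group and lean-mass change. If BMD is modelled as repeated values, use the lean-mass change × group × time term with its lower-order terms; a two-way lean mass × group term would then describe BMD level.
3. Report the within-romosozumab slope with a 95% CI as the estimate for gainers versus non-gainers, with the placebo slope beside it, and say that the slope replaces a gainer cut-point for this question.
4. For the placebo-lowest part, report mean BMD change in romosozumab women without lean-mass gain (change ≤ 0) minus that in all placebo women, with a 95% CI. Do not substitute the difference at exactly zero lean-mass change.
5. Label all of these exploratory and associational, since lean-mass change is observed after randomization.

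The cost is a few sentences, settled before unblinding, with no new data or visits. The downside is two or three more exploratory estimates, all imprecise.
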